6.3 Study procedures

6.3.1 Recruitment

- 6.3.1.1 Potentially eligible patients will be recruited from the Wake Forest Comprehensive Cancer Center
- 6.3.1.2 The research nurse (RN) will be contacted to review eligibility and to consent eligible patients in person.
- 6.3.1.3 The RN will obtain baseline surveys, clinical information and ensure research labs are drawn and processed per protocol. Pill dairy will be provided at each visit.
- 6.3.1.4 Study drug (30-day supply) will be provided to participant by the RN.

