11.0 Data Management

12.0 Statistical Considerations

12.1 Analysis of Primary Objective

The primary objective of determining the safety and MTD of MGE will be completed by monitoring toxicities and using the dose escalation plan detailed above.

To determine the maximum tolerated dose (MTD) of MGE in patients with metastatic cancer, we will use a standard 3+3 Phase 1 dose escalation statistical design. All MGE dose escalations conducted will be escalated according to the dose escalation scheme (see Section 6.2). The number of patients in each cohort will be 3. If no patients in any cohort develop a dose-limiting toxicity (DLT), dose escalation will continue in cohorts of 3 patients up to the maximum dose. However, if a DLT is observed in 1 of 3 patients at any dose level, the cohort of that dose level will be expanded to a maximum of 6 patients. If 1 of the 6 patients has a DLT, the dose escalation procedure will continue in 3 patients for each subsequent cohort. However, once a DLT is observed in a total of 2 patients at any dose level. dosing of MGE in patients at that dose level will stop immediately, even though the total number of patients at the last cohort may be as few as 2. Dose escalation is considered to be complete. The dose level that induces a DLT in 2 or more patients is considered to be above MTD, and the dose level immediately below the dose level that induced a DLT in ≥2 patients is considered the MTD for MGE if ≤1 participants of 6 patients at that level have a DLT.

In the event that the MTD is not observed after the 5 dose levels listed in Section 6.2 have been tested, the investigators will consider stopping additional dose escalation. The decision will be based on the actual dose level tested, the extent of anti-tumor efficacy observed, and the type of toxicity observed, etc.

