12.2 Analysis of Secondary Objective

12.2.1 To monitor toxicity at 4, 8, and every 4 weeks thereafter on MGE

To analyze objective 2.1.1, we will summarize any expected toxicities, any laboratory based toxicities, and any grade 3 or higher gastrointestinal toxicities and any grade 4 or higher toxicities using frequency tables overall and by week.

12.2.2 To evaluate change in phenolic levels (total and component, blood and urine) from baseline to 4 and 8 weeks

To analyze objective 2.2.2, we will fit a mixed model ANOVA model with phenolic level as the outcome and time (baseline, 4, and 8 weeks) as a fixed effect and subject as a random effect. We will use contrasts to estimate the changes from baseline to week 4 and week 8.

12.2.3 To evaluate change in serum cytokines and growth factors from baseline to 4 and 8 weeks on MGE

To analyze objective 2.2.3, we will fit a mixed model ANOVA model with the outcome of interest (cytokine or growth factor) as the outcome and time (baseline, 4, and 8 weeks) as a fixed effect and subject as a random effect.

We will use contrasts to estimate the changes from baseline to week 4 and week 8.

12.2.4 To observe the response rate of MGE in patients with metastatic cancer.

To analyze objective 2.2.4, we will characterize response at 8 weeks using frequency table. We will also characterize the best response at the end of treatment with MGE using a frequency table.

12.2.5 To assess overall and progression-free survival in patients with metastatic cancer receiving MGE.

To analyze objective 2.2.5, we will summarize overall survival and progression-free survival using the Kaplan-Meier method. We will calculate median survival rates and associated 95% confidence intervals. Patients will be censored at date of last contact.

12.2.6 To assess global quality of life and fatigue in cancer patients taking MGE.

Quality of Life and fatigue will be monitored every 4 weeks until the end of the study. To analyze objective 2.2.6, we will fit a mixed model ANOVA model with phenolic level as the outcome and time (baseline, every 4 weeks) as a fixed effect and subject as a random effect. We will use contrasts to estimate the changes from baseline to each follow-up time period.

12.2.7 To assess adherence to MGE treatment.

To analyze objective 2.2.7, we will summarize the percent of pills taken at the end of every 4 week period i using the formula:

Percent of pills taken_i =

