$$\frac{(Dose \ Level \ \times \ 7 \ \times \ 4)_i - Pill \ Count_i}{(Dose \ Level \ \times \ 7 \ \times \ 4)_i}$$

In the formula above, pill count will be calculated from counting the number of pills returned as well as by summarizing the patient's pill diary. The percent of pills taken will be summarized by dose level using the mean and 95% confidence interval.

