12.3 Power and Sample Size

The study will enroll a minimum of 2 participants and a maximum of 30.

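### A mean with a 95% confidence interval for adherence at each dose level is uninformative with 2 to 6 patients and a capped outcome: it can pass 100% or collapse to zero width (minor)

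*Combined protocol and SAP*

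**What the plan says.** For objective 2.2.7, section 12.2.7 states that "we will summarize the percent of pills taken at the end of every 4 week period". It takes the share from a printed formula whose denominator is Dose Level × 7 × 4, and adds that "The percent of pills taken will be summarized by dose level using the mean and 95% confidence interval". No interval method, transformation, bound, median, range or patient listing is given, and no expected adherence or SD.

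Section 12.1 fixes the size of each level. The starting rule is "The number of patients in each cohort will be 3". After one DLT in three, "the cohort of that dose level will be expanded to a maximum of 6 patients". When dosing stops on a second DLT, "the total number of patients at the last cohort may be as few as 2". Section 12.3 adds: "The study will enroll a minimum of 2 participants and a maximum of 30".

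On the measurement itself, "pill count will be calculated from counting the number of pills returned", together with the pill diary. Section 6.2 sets twice-daily dosing, and section 6.3.1 says "Study drug (30-day supply) will be provided to participant by the RN".

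**The concern.** A standard interval for a mean relies on enough observations, or on roughly normal data. Here there are two to six values per level. The outcome has a ceiling, because returned pills cannot be fewer than zero, and many patients may sit at or near it. The number per level can only fall in later 4-week periods as patients leave treatment, and with one patient left no interval exists.

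Two outputs are then possible that no reader can use: an upper limit above 100%, or a zero-width interval that looks like perfect precision. At stake is how adherence at each pill burden is reported. The trial's conduct is not affected.

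**Working it through.** **Plan's own figure.** 5 dose levels (section 6.2) × 6 patients (section 12.1) = 30, which reproduces the maximum in section 12.3. So 3 to 6 per level, with 2 possible in the last cohort, is the right range.

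**Interval width.** Assume a t-interval: mean ± t(0.975, n−1) × SD/√n. Half-width in SD units:

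- n=2: 12.706/√2 = 8.98
- n=3: 4.303/√3 = 2.48
- n=4: 3.182/√4 = 1.59
- n=5: 2.776/√5 = 1.24
- n=6: 2.571/√6 = 1.05

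**Examples that need no assumed distribution.**

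- n=3, values 100, 95, 85%: mean 93.3, SD 7.64, half-width 2.48 × 7.64 = 19.0, interval 74.4% to 112.3%.
- n=3, all at 100%: SD 0, interval 100% to 100%.
- n=6, values 100, 100, 100, 95, 95, 85%: mean 95.8, SD 5.85, half-width 6.1, interval 89.7% to 102.0%.

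**How often, under assumptions.** The documents give no adherence distribution. I assumed beta distributions on the scale of pills taken as a share of pills prescribed, with 200,000 simulated levels per cell and the t-interval.

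| Mean / SD (points) | Coverage, n=3 | Upper limit >100%, n=3 | Coverage, n=6 | Upper limit >100%, n=6 |
|---|---|---|---|---|
| 80 / 10 | 94% | 55% | 94% | 0.3% |
| 80 / 15 | 92% | 80% | 92% | 14% |
| 80 / 20 | 88% | 91% | 90% | 49% |
| 85 / 10 | 93% | 73% | 93% | 6% |
| 85 / 15 | 88% | 90% | 89% | 45% |
| 85 / 20 | 81% | 96% | 85% | 80% |
| 90 / 10 | 88% | 89% | 89% | 42% |
| 90 / 15 | 78% | 97% | 82% | 85% |
| 90 / 20 | 63% | 99% | 73% | 97% |

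**Zero width.** If half of patients take every pill, all n do so with probability 0.5ⁿ: 12.5% at n=3 and 1.6% at n=6.

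**Scale of the printed formula.** Read Dose Level as the level number L. Prescribed pills over 28 days are 2L × 28 = 56L, and the 30-day supply is 60L. If a is the share of prescribed pills taken and all leftovers are returned, returns are 60L − 56La, so the printed score is (28L − 60L + 56La)/28L = 2a − 8/7. A fully adherent patient (a=1) scores 85.7%, and one who took half the pills scores −14%. With 56L as denominator, full adherence scores 52/56 = 92.9%. At a given level the score is linear in a, so coverage and zero-width rates do not change. The interval passes the full-adherence score of 85.7% as often as the table shows for 100%. It passes 100% itself less often: 24–53% at n=3 and 0–41% at n=6 over five assumed distributions (smooth beta with mean 80, 90 or 95%, half of patients at exactly 100%, and a mixture of good and poor takers).

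**The case against.** The strongest reply is that this is the last-listed secondary objective, purely descriptive, and that the plan does not commit to a t-interval, so a bounded method is not excluded. That stands, and it is why the point is minor. It does not remove the point: with no method named, the t-interval is the natural default, and no method extracts much precision from three values.

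A reader might infer three stronger things that the documents do not support.

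- *That the intervals usually run above 100% and cover well below 95%.* At n=3 the first part holds across the assumed grid, but at n=6 exceedance runs from 0.3% to 97%. Coverage is 92–94% in the milder cells. Severe shortfall needs strong skew, a pile-up at 100%, a subgroup of poor takers, or a normal-quantile interval. On the printed scale, passing 100% is not assured to be usual even at n=3.
- *That the interval informs dose selection.* Section 1.2 cites compliance when it sets the dose range, but that choice was made before the trial. Escalation and the MTD rest on DLTs (sections 6.2.1 and 12.1), and no comparison of adherence between levels is planned.
- *That repeated periods are pooled as if independent.* Section 12.2.7 indexes the percentage by 4-week period, which points to one value per patient per period. The sentence on dose levels does not repeat this, so a clarifying word helps, but pooling is not stated.

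**Conclusion.** The concern holds in a limited form. A mean with a 95% interval per dose level, from 3 to 6 patients (possibly 2) on a capped outcome, can give impossible upper limits or false certainty. The two n=3 examples show this without assuming a distribution. The rates are conditional on a t-interval, on beta-distributed adherence with mean 80–90% and SD 10–20 points, and on adherence as a share of prescribed pills. Under those assumptions coverage ranges from close to nominal (94%) down to 63% at n=3 and 73% at n=6. The importance is minor: the harm is confined to misleading reporting of objective 2.2.7.

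The printed denominator is a separate matter. If Dose Level means the level number, it does not match twice-daily dosing. Whether or not it does, 28 days do not match a 30-day supply when returned pills are subtracted.

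**What to change.** Replace the last sentence of section 12.2.7 with wording such as: *For each dose level and 4-week period, each patient's percent of pills taken will be listed, with the median and range and no confidence interval. One 95% confidence interval for mean adherence will be given pooled over dose levels, with the patient as the unit, using a method bounded to 0–100% (for example a patient-level bootstrap).*

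This changes one sentence and needs no new data. The cost is that no per-level interval is shown, and that the pooled interval describes the mix of levels actually enrolled. The listing still shows every value at each level. If the trial stops after only a handful of patients, the listing alone is enough.

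Separately, the formula in section 12.2.7, the schedule in section 6.2 and the supply in sections 6.3.1 and 6.3.2 must be reconciled before any adherence percentage is reported.

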12.3 Power and Sample Size

The study will enroll a minimum of 2 participants and a maximum of 30.

12.4 Estimated Accrual Rate and Study Length

We anticipate accruing at least 2 patients per month on this protocol and thus expect that accrual for this Phase 1 trial will be completed in less than 16 months, and that the MTD can be determined within 1 month of the last accrual. Patients will be followed until death.

Appendix A – Protocol Registration Form

See separate attachment in the eIRB under Protocol Document.

Appendix B – Subject Eligibility Checklist

See separate attachment in the eIRB under Protocol Document

Appendix C – Mandatory STRC SAE Reporting Guidelines

See separate attachment in the eIRB under Protocol Document

Appendix D – Treatment Response Evaluation

See separate attachment in the eIRB under Protocol Document.

Appendix E – End of Treatment Evaluation of Best Overall Response

See separate attachment in the eIRB under *Protocol Document*.

Appendix F – FACT-G

See separate attachment in the eIRB under Protocol Document.

Appendix G – PROMIS-Fatigue SF

See separate attachment in the eIRB under Protocol Document.

Appendix H – Daily Pill Diary

See separate attachment in the eIRB under Protocol Document

Appendix I – Baseline Data Collection Form

See separate attachment in the eIRB under Protocol Document

CBC results will be drawn directly into the database from ORIS. Do not abstract them from the medical record. Results will include WBC, RBC, Hemoglobin, Hematocrit, MCV, Neutrophils, Lymphocytes, Platelets.

Serum chemistry results will be drawn directly into the database from ORIS. Do not abstract them from the medical record. Results will include Albumin, Alkaline phosphatase, Total bilirubin, Bicarbonate, BUN, Calcium, Chloride, Creatinine, Glucose, Potassium, Total protein, SGOT[AST], SGPT[ALT], Sodium.

Cancer-specific tumor marker values will be drawn directly into the database from ORIS. Do not abstract them from the medical record.

Appendix J – Follow-Up Data Collection Form

See separate attachment in the eIRB under *Protocol Document*

CBC results will be drawn directly into the database from ORIS. Do not abstract them from the medical record. Results will include WBC, RBC, Hemoglobin, Hematocrit, MCV, Neutrophils, Lymphocytes, Platelets.

Serum chemistry results will be drawn directly into the database from ORIS. Do not abstract them from the medical record. Results will include Albumin, Alkaline phosphatase, Total bilirubin, Bicarbonate, BUN, Calcium, Chloride, Creatinine, Glucose, Potassium, Total protein, SGOT[AST], SGPT[ALT], Sodium.

Cancer-specific tumor marker values will be drawn directly into the database from ORIS. Do not abstract them from the medical record.

Appendix K – Correlative Research Labs Data Collection Form

See separate attachment in the eIRB under Protocol Document

Appendix L – Telephone Follow-Up Form

See separate attachment in the eIRB under Protocol Document

Appendix M – Off Study Documentation Form

See separate attachment in the eIRB under Protocol Document

Appendix N – Follow-Up Form for Survival

See separate attachment in the eIRB under Protocol Document

Appendix O – Adverse Event Log

See separate attachment in the eIRB under Protocol Document

Appendix P – Physician Order Form for Study Drug

See separate attachment in the eIRB under *Protocol Document*
